# 3.9 Data Collection and Management:3.9.1 Data collection tool

To ensure consistency and minimization of errors in the data collected, standardized methods of data management will be used by the study team.

**Data Collection Procedures:** Base line data will be collected from study participants in the intervention and control group. This will be before the introduction of the intervention. At baseline data collection, informed consent, questionnaires on comprehensive medical history, dietary intake, smoking and alcohol intake, medication use, physical activity, anthropometry, BP, FBS and lipid profile tests will be undertaken for all participants.

After the introduction of the intervention, data will be collected serially from study participants in the intervention arm on selected variables before the group sessions to monitor adherence of participants to the intervention. Final end-line data similar to data collected at baseline will be collected in both the intervention and non-intervention arms. In control group, the participants who have baseline data will be considered in analysis for comparison purposes.

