#### Package of the group physical activity intervention sessions

Group physical activity sessions will cover a range of topics, including the different physical activity types, the importance of physical activity, and ways to incorporate physical activity into daily life, the WHO recommendations for physical activity and simple physical activity routines, the levels of physical activity and strategies to increase it, the risks associated with physical activity, exercise safety, and injury prevention, overcoming common barriers to exercise, staying motivated, nutrition for physical activity, and monitoring progress with exercise logs. Participants will receive encouragement to perform a minimum of 150 minutes of moderate-intensity or 75 minutes of vigorous-intensity aerobic physical activity per week, which includes activities like running, climbing stairs, and participating in sports. Additionally, participants will be encouraged to actively participate in muscle-strengthening activities, such as going to the gym, lifting heavy objects, or practicing yoga, for a minimum of two days per week, at a moderate level of intensity. Participants will receive guidance to decrease sedentary behavior by substituting it with any level of physical activity. Participants will receive leaflets containing key messages for their reference.

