#### **3.10 Ethical Considerations**

Approval will be sought from by the MakSPH Higher Degree's Research and Ethical Committee (HDREC) and Uganda National Council of Science and Technology (UNCST). All participants will be informed about the purpose of the study and the use of resulting data. Consent will be obtained from all respondents. All participants will sign a voluntary informed consent form for being included study. Assigned copy of the informed consent will be given to each participant after the interview. For participants under 18 years, we will seek consent of their legal guardians and assent of the participants.

Confidentiality will be always observed by only allowing investigators to access the data. Electronic or hard copies of data will be stored securely. Anonymity of respondents will be ensured by using codes as identifiers.

Participants in intervention group will be informed about the risks associated with intervention including discomfort of finger prick and venepunctures, possible discomfort and dizziness following physical activity. The study team will ensure that participant safety, privacy and confidentiality are ensured during the intervention sessions.

The participants in the control group will be given information about the principles of a healthy lifestyle from study team.

Female nurses and female graduate medical students will conduct waist circumference measurements. Qualified laboratory technicians will conduct finger pricks and venipunctures.

All newly detected NCD patients will be given a referral form to attend the nearest health center for further management.

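### The protocol names harms of physical activity but states no item, in either arm, that asks about them, so a reliable between-arm statement on these harms is not possible.

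*Protocol*

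**What the plan says.** Section 3.10 (Ethical Considerations) states: "Participants in intervention group will be informed about the risks associated with intervention". The risks it lists are "discomfort of finger prick and venepunctures, possible discomfort and dizziness following physical activity". It then gives a general commitment: "The study team will ensure that participant safety, privacy and confidentiality are ensured during the intervention sessions". Under section 3.3, the physical activity package includes as teaching topics "the risks associated with physical activity, exercise safety, and injury prevention".

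Data collection is set out in section 3.9.1. Baseline, in both arms, consists of "questionnaires on comprehensive medical history, dietary intake, smoking and alcohol intake, medication use, physical activity, anthropometry, BP, FBS and lipid profile tests". Between baseline and endline, "data will be collected serially from study participants in the intervention arm on selected variables before the group sessions to monitor adherence"; the variables are not listed. At the end, "Final end-line data similar to data collected at baseline will be collected in both the intervention and non-intervention arms".

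The secondary outcomes in section 3.6 cover diet, anthropometry, cardio-metabolic measures, nutrition knowledge and lifestyle. The Data Analysis text drops women who attend fewer than 60% of their intervention sessions.

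**The concern.** The protocol identifies harms that the intervention may cause and tells the intervention group about them, but states no means of counting them. The serial collection has adherence as its purpose and leaves out the controls, so any event mentioned in passing would come from one arm only. Endline covers both arms but is modelled on a baseline set that, as described, has no question on what happened during the 12 weeks.

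Section 1.2 gives informing policy on preventing and managing metabolic syndrome as the trial's purpose. A report of benefit with no harm count, no denominator and no comparison with controls serves that purpose less well. This is not a matter for a later analysis plan: what is asked, of whom and when belongs in the protocol.

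The attendance rule adds to the problem. Only the intervention arm has sessions to attend, so a woman who stopped because she was hurt or unwell could be removed from that arm's analysis, and the rule has no counterpart among controls.

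**Working it through.** The protocol gives no figure on harm, so there is none to reproduce. The check is a reading of each stated contact and analysis, followed by arithmetic for scale.

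**Contact by contact**

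- Baseline, both arms (3.9.1): medical history, medication use, behaviour, measurements and blood tests. It precedes exposure, so it cannot record harm from the intervention.
- Serial collection before group sessions (3.9.1): intervention arm only, variables unlisted, purpose adherence.
- Adherence monitoring (3.8): questionnaires and attendance registration, again for adherence.
- 24-hour recall before and after counselling (3.9, Dietary measurements): diet.
- Endline, both arms (3.9.1): similar to baseline. The history spelled out under Socio-demographic characteristics concerns diabetes, hypertension, obesity and dyslipidaemia. No question on events since baseline is stated.
- Secondary outcomes (3.6) and Data Analysis (3.9): no safety outcome and no safety analysis.

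No contact therefore has a stated harm item. Endline is the only contact after exposure with stated data collection in both arms.

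**What systematic asking would allow**

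Inputs: 60 women per arm (section 3.7). The same section allows 10% for dropout and failure to consent; applied to one arm as an assumption, this leaves 60 × 0.90 = 54.

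Exact one-sided 95% upper limit when no event is seen in n women: 1 − 0.05^(1/n).

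- n = 60: 1 − 0.05^(1/60) = 0.0487, or 4.9%.
- n = 54: 1 − 0.05^(1/54) = 0.0540, or 5.4%.

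Probability of at least one event in 60 women at true risk p: 1 − (1 − p)^60. The protocol gives no risk, so these values of p are assumptions.

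- p = 1%: 45%
- p = 2%: 70%
- p = 5%: 95%
- p = 10%: 99.8%

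These are one-arm figures that hold only if every woman is asked. They show what asking could establish about the intervention arm. They do not measure the precision of a comparison with controls.

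**The case against.** The strongest case on the other side is that the gap is inferred from silence. The questionnaires are not reproduced in the protocol, so their items cannot be known. The selected variables in the serial collection are unlisted, and a form completed before one session can ask about the session before it, so the timing does not rule out capture of harms. Endline repeats a medical history and medication use in both arms, so a new illness or lasting injury could appear there. The intervention is low-risk, women whose diseases could be worsened by the sessions are excluded (3.4), injury prevention is taught, and the objectives claim no comparison of harms.

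Much of this stands, and it limits the point. A reader might infer that harms can be recorded nowhere and that the trial can say nothing about them. The documents do not support that, because endline remains a possible route for serious or lasting events. Nor do they support describing the encouraged activity as unsupervised or done at home; section 3.3 uses neither term. It would also be wrong to count 12 weekly plus 3 monthly sessions as 15 missed chances to observe activity harm: those are nutrition and motivational interviewing sessions, and the number of physical activity sessions is not stated.

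What does not stand is the suggestion that these possibilities fill the gap. An unlisted variable collected for adherence in one arm is not a plan to collect harms. A general medical history is a poor instrument for dizziness weeks earlier. That the objectives claim no harm comparison does not remove the need, since the protocol itself names the risks.

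**Conclusion.** The point holds in a limited form. The protocol names discomfort and dizziness after physical activity as risks but specifies no systematic harm collection that is comparable between arms. Serious or lasting events might surface at endline; transient or healed ones probably would not. The trial as written cannot make a reliable between-arm statement on activity harms.

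In size, the loss is that the trial could not give even the modest bound available from 60 or 54 women asked with no event (4.9% or 5.4%). The conclusion assumes that the questionnaires contain no event item beyond what the protocol describes. If one exists, the protocol should state it, and the remaining matters would be its use in both arms and the attendance exclusion. The primary outcome is unaffected, but the gap cannot be properly repaired once endline interviews are complete, so the change should be made before then.

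**What to change.** Add to the existing ODK endline questionnaire, in both arms, one fixed block with a 12-week recall period covering injury, fainting or dizziness, and any health facility visit or admission. Report it by arm, with denominators, for every randomised woman who has an endline interview, and state that the 60% attendance exclusion does not apply to this summary.

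Optionally, add one event question to the existing pre-session form and report it descriptively for the intervention arm only, outside the between-arm comparison. Who acts on a positive answer is for the sponsor to specify.

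The cost of the endline block is a few items on a form already in use, with no added visit. The drawback is recall. Minor events will be under-reported, and not necessarily to the same degree in each arm: participants may not be blinded (section 3.7, Blinding), and the protocol provides for telling only the intervention group about these risks. Repeated pre-session questions could widen that difference. The report should state this caveat beside the comparison.

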#### Socio-demographic characteristics

A standardized interviewer-administered questionnaire will be adopted to obtain data on socio-demographic factors, behavioral factors (smoking status, alcohol intake, physically active or not) and history of NCDs like Diabetes, hypertension, obesity and dyslipidemia. A questionnaire will be administered for analysis of the daily consumption and type of foods eaten at breakfast, or as snacks, at lunch and super.

#### **Dietary measurements**

Initial and follow-up visits will include anthropometrical data, biochemical parameters, and assessment of current diet.

The 24 h recall questionnaire will be used before and after nutritional counseling and evaluated for the presence or absence of changes in eating habits. The food frequency questionnaire (FFQ) will be used at baseline and end line.

Nutritional analysis will be carried out with software ENA for Smart. Table of Food Composition will be used to determine the macro and micronutrients content of foods.

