#### Secondary outcomes

The secondary outcome will be the within - and between group variations in each of the following variable measured.

- dietary habits and behaviors (salt intake, fruits and vegetables intake, fat intake,
- anthropometric (weight, WC and BMI)
- cardio-metabolic (hypertension, blood glucose, triglycerides, HDL)
- nutrition knowledge
- lifestyle (physical activity, alcohol intake, cigarette smoking)

Mean change in parameters across the comparison and intervention groups will be determined. The measurement of the outcomes will be conducted before and at the end of the activities to determine the effect of the intervention.

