#### **Data Analysis**

The data for participants who attend less than 60 % of their respective intervention sessions will be excluded from analyses.

Participants with attendance rates below 60% in the intervention sessions will not be included in the analyses.

The analyses will be conducted using Stata statistical software (SE/ 14.0, StataCorp, College Station, TX, USA. Variables will be expressed using descriptive analysis (means and SD). The baseline information for both comparison and intervention groups will be statistically compared regarding all influencing factors at baseline and end line (12 weeks). The chi-square test will analyse for differences in categorical outcomes, including baseline study characteristics, metabolic risk factors (waist circumference (WC), blood pressure (BP), triglycerides, fasting blood sugar(FBS), and high-density lipoprotein (HDL) Cholesterol),

and other factors including dietary habits such as fruits and vegetable intake, and food groups consumed. Behaviours, including smoking, alcohol intake, and physical activity, will also be analysed.

The Student T test for independent samples and variance analysis (ANOVA) will compare cardio-metabolic parameters (and their variations - to find any differences between findings) between the intervention group and the comparison group at the baseline and end of the intervention (after-before).

A 2 factor (2 x 2; group x time) repeated measures analysis of variance (ANOVA) will be performed for each dependent variable and a 1-way ANOVA will be used to assess the significance of differences between groups on the dependent variables assessed. Tukey's post hoc analysis will be performed if there is a significant finding. The T test for paired data will be applied to investigate within –group variable variations (after-before). Statistical significance will be set at p < 0.05.

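### The protocol defines the secondary diet outcomes as mean change but evaluates the 24 h recall as change present or absent, without direction or threshold, and does not say which instrument or scoring supplies the outcome

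*Protocol*

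**What the plan says.** Three places in the protocol bear on how diet is measured and compared.

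- **Section 3.6, Secondary outcomes.** The list includes "dietary habits and behaviors (salt intake, fruits and vegetables intake, fat intake". The summary for the list is "Mean change in parameters across the comparison and intervention groups will be determined". This treats each intake as a quantity.
- **Section 3.9, Dietary measurements.** "The 24 h recall questionnaire will be used before and after nutritional counseling", and it is then "evaluated for the presence or absence of changes in eating habits". No food item, direction or size of change is given, nor the number of recall days at each time point. The same section adds a second instrument, "The food frequency questionnaire (FFQ) will be used at baseline and end line", and a quantitative step, "Table of Food Composition will be used to determine the macro and micronutrients content of foods".
- **Section 3.9, Data Analysis.** The chi-square test for categorical outcomes covers the metabolic risk factors and "other factors including dietary habits such as fruits and vegetable intake, and food groups consumed". The between-arm t test is written for cardio-metabolic parameters, and the mixed model names only the five metabolic components. The group-by-time repeated-measures ANOVA is planned for every dependent variable and could therefore include diet.

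Dietary intake is named in the secondary objective (2.2.2). The nutrition education package in section 3.3 gives an intended direction for each food: more of some, less of others.

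**The concern.** The outcome list calls for a quantity, while the measurement section describes a yes/no evaluation of one of the two diet instruments. No sentence connects either instrument to the outcome. Two analysts could follow the protocol faithfully and report different diet results, and the choice could be made after the data are seen.

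The yes/no wording is also the weaker option. Read literally, a woman who eats less fruit has changed just as much as one who eats more, although the intervention aims only at the second. Ordinary day-to-day variation produces such changes in both arms. At stake is the evidence on a behaviour that the programme directly targets. The primary outcome, metabolic syndrome prevalence at 3 months, is not touched.

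**Working it through.** The protocol gives no effect size, variance or power for diet, so there is no stated figure to reproduce. What follows is an illustration under assumptions.

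**Inputs from the protocol.** 60 women per arm and 10% loss (section 3.7): 60 × 0.9 = 54 per arm. Two-sided 5% level assumed, since section 3.7 does not state sidedness.

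**Assumed inputs.** Usual fruit and vegetable intake averages 2 servings a day, with a between-woman coefficient of variation of 0.5 (variance 1, gamma). One recall day per time point, Poisson around usual intake. True gain of 1 serving a day in the intervention arm, none in controls.

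**Mean change, by hand.**
- Variance of change: controls 2 + 2 = 4; intervention 2 + 3 = 5.
- Standard error of the difference: √(4/54 + 5/54) = 0.408.
- Power: Φ(1/0.408 − 1.96) = Φ(0.49) = about 69%. Simulation gives 68%.

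**Baseline-adjusted end-line mean, by hand.**
- Baseline variance 2 + 1 = 3; covariance of baseline with end line 1; slope 1/3.
- Residual variance: controls 3 − 1/3 = 2.67; intervention 4 − 1/3 = 3.67.
- Standard error: √((2.67 + 3.67)/54) = 0.343.
- Power: Φ(1/0.343 − 1.96) = Φ(0.96) = about 83%. Simulation gives 82% to 83%.

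**Direction-free yes/no, by simulation.** A woman counts as changed if her two recalls differ by at least the threshold in either direction.

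| Threshold (servings) | Controls changed | Intervention changed | Power, chi-square |
|---|---|---|---|
| 1 | 77% | 82% | 11% |
| 2 | 40% | 51% | 19% to 20% |
| 3 | 19% | 29% | 22% to 23% |

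Hand check of the first row, with unrounded shares 0.765 and 0.824: difference 0.059, pooled proportion 0.795, standard error √(0.795 × 0.205 × 2/54) = 0.078. The ratio is 0.76 and power about 12%.

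**Sensitivity to the assumed mean.** With means of 1.5 to 3 servings, mean change has about 53% to 79% power. The direction-free score has 8% to 17% at a threshold of 1 serving and at most 31% at the higher thresholds.

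**A different model.** Take the change score as normal with a shift of 0.5 SD and 52 women per arm. Power is 72% for mean change and 4% to 10% for direction-free change at thresholds of 0.1 to 1.5 SD. The share of controls counted as changed runs from 92% down to 13%.

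**Type I error.** With no true effect all the tests reject at about 5%, so the difference between them is one of power only.

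**The case against.** The strongest reply is that the protocol never makes changed/unchanged an endpoint. The phrase under Dietary measurements may only state why the recall is repeated. Outcomes are defined in section 3.6, as mean change in named intakes, and the food composition step is quantitative. The chi-square sentence also lists waist circumference, blood pressure and lipids, which are analysed by means as well, so appearing there does not rule out a mean analysis. No sentence sends a changed/unchanged score to the chi-square. A score counted only in the intended direction would do much better: about 51% to 61% power at the same thresholds. Coding of secondary variables is, moreover, often left to the statistical analysis plan.

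Much of this stands, and it is why the point is conditional on how the recall is scored. It does not remove the mismatch: the protocol states a yes/no evaluation beside a mean-change outcome and leaves the source of the outcome open.

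Three stronger readings are tempting and not supported.
- **That most controls would count as changed.** This depends on a threshold that the protocol does not set; the share runs from 77% to 19% in the servings model.
- **That the diet effect would be largely hidden.** The FFQ is planned at baseline and end line, similar end-line data are collected in both arms, and the mean-change summary remains.
- **That physical activity has the same fault.** The protocol refers to a modified STEPS questionnaire and lists IPAQ among its abbreviations, but the items are not shown, so minutes of activity may well be recorded.

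**Conclusion.** The point holds as a mismatch to be resolved. Section 3.6 fixes mean change, the Dietary measurements section fixes presence or absence of change for the recall without direction or threshold, and the Data Analysis section lists fruit and vegetable intake under the chi-square. The instrument and scoring behind the outcome are not stated.

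The cost of taking the direction-free option is large under the assumptions used: about 11% to 22% power, against 68% for mean change and 82% for the baseline-adjusted mean. The ordering held at every threshold and mean tried and under both models; the exact figures rest on the assumed intake distribution, a single recall day and the assumed gain. They describe a quantity taken from the recall and do not forecast the precision of the FFQ. The importance is moderate: secondary outcomes only, with no effect on the primary outcome or the sample size.

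**What to change.** - **Dietary measurements:** replace the presence-or-absence evaluation with quantitative intake of each named item (for example, servings of fruit and vegetables per day). Name the FFQ as the source of the secondary diet outcomes and the 24 h recall as supportive. If the FFQ as fielded cannot quantify one of the intakes, name the source for that item.
- **Analysis:** compare end-line intake between arms, adjusted for baseline intake, and report the adjusted mean difference with its confidence interval.
- **Data Analysis:** keep the chi-square only for truly categorical diet items, such as food groups consumed.

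The cost is wording in two subsections. No visit or procedure is added, since the FFQ is already planned at both time points. The small downside is that any yes/no summary of change becomes descriptive.
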